1.0 Study synopsis

This is a Phase II pilot exploratory study designed to investigate if prophylactic treatment with short term steroids administered to high risk Covid-19 patients might prevent cytokine storm and progression to respiratory failure. It is also designed to determine if it is feasible to identify a subset of cases with low risk for complications that can be observed as outpatients without treatment. High risk is defined based on serologic markers of inflammation that include abnormalities of IL-6, ferritin, D-dimer, LDH, as well as lymphopenia and impaired O_2 saturation prior to or on the 7^{th} - 10^{th} day of first symptom of Covid-19.

1.1 This is a non-randomized study which will be carried out at Auxilio Mutuo and possibly at other institutions to be recruited.

2.0 Schedule of Study Assessments

- 2.1 At, or prior to, entry into study:
 - 2.1.1 History and Physical exam
 - 2.1.2 Labs: CBC, CMP, LDH, arterial blood gases, serum IL-6, serum ferritin, CRP, D-dimers, troponin
 - 2.1.3 Radiologic studies: CT chest without IV contrast preferably prior to treatment with methylprednisolone.
 - 2.1.4 Other studies:
 - 2.1.4.1 Either PCR for molecular detection of SARS-Cov-2 virus and serologic rapid test (IgG, IgM), or both (see figure 2). Cases who are IgG positive but IgM negative, will not be considered eligible unless they are positive by molecular PCR test or they are acutely ill with symptoms typical of Covid-19 (see section 6.2 for typical symptoms).
 - 2.1.4.2 O₂ saturation by pulse oximetry
 - 2.1.4.3 Influenza rapid test if considered necessary.
- 2.2 During study (only applies to those eligible for treatment with methylprednisolone):
 - 2.2.1 For patients admitted to hospital: Vital signs q 8 hours (not q 4 hrs) to reduce chance of nursing staff contamination
 - 2.2.2 Day 7-10 from first symptom of illness: CBC, CMP, LDH, serum IL-6, serum ferritin, CRP, d-dimers
 - 2.2.3 Day 14 from registration on trial:

- 2.2.3.1 repeat CBC, CMP, LDH, serum IL-6, serum ferritin, CRP, d-dimers
- 2.2.3.2 repeat PCR for molecular detection of SARS-Cov-2 virus
- 2.2.4 Day 28 from registration on trial:
 - 2.2.4.1 repeat CBC, CMP, LDH, serum IL-6, serum ferritin, CRP, d-dimers
 - 2.2.4.2 repeat PCR for molecular detection of SARS-Cov-2 virus
 - 2.2.4.3 CT chest without IV contrast

[figure not shown]
3.0 Background and Rationale

The management of Covid-19 with mild manifestations has usually been conservative. Traditionally, treatment has consisted of observation at home provided there is no shortness of breath or evidence of pneumonia. Front line therapy with Hydroxychloroquine (Plaquenil) combined with Azithromycin has been used with preliminary positive results[1]. Plasma therapy has been successfully used in a small number of cases[2]. Vitamin C has also been utilized, although no definitive results are available[3].

Covid-19 is a triphasic disorder typified by a first infectious phase that lasts from the first onset of symptoms until 7-10 days later when it is followed by a second phase considered as the inflammatory or pulmonary phase with appearance of lung infiltrates which is later followed by a hyperinflammation phase characterized by Acute Respiratory Distress Syndrome (ARDS), shock and cardiac failure. For unclear reasons, patients do not always proceed to develop the second or third phase and are spontaneously cured after the first phase. Figure 1

Figure 1

Basics of COVID19 infections

[figure not shown]

5 Siddiqi & Mehra, J Heart Lung Transpl (2020). Epub ahead of print: https://doi.org/10.1016/j.healun.2020.03.012

This second phase is heralded by an elevation of certain serologic markers of inflammation such as IL-6, CRP, LDH and ferritin as well as D-dimers[4, 5]. See figure 2

It is not clear why some patients enter this second phase of the disease while others do not, but what is clear is that the second or inflammatory phase is caused by pulmonary macrophage activation with subsequent release of the inflammatory mediators. These molecules will damage the capillary-alveolar membrane eventually causing respiratory insufficiency. These are the patients that frequently will require ventilatory support and eventually most will die. This second and third phase are in great part due to activation of the patient's immune system while the first phase is mostly mediated by the viral infection itself.

Figure 2 *

*Red line represents patients who died while blue line represents survivors. The x axis represents number of days after onset of illness.

Usually anti-inflammatory therapy with an anti-IL-6 antibody, Tocilizumab, is reserved for patients who are evolving poorly, especially patients with severe pneumonia with elevated IL-6 serum levels [6]. However, once these patients have pneumonia, anti-inflammatory treatment is usually not very successful. Nevertheless, the use of methylprednisolone has been associated with substantial reduction of risk of death even if administered late, when patients already have ARDS[7]. However, if given late, the probability of dying is 52%[7].

[name], from Hospital Peset, in Valencia, Spain has developed an approach designed to anticipate the second, or so-called inflammatory phase. He has proposed that when the pulmonary infiltrates appear, this is no longer an infectious process, but it is purely an inflammatory or immune issue which causes anatomical injury to the capillary alveolar membrane resulting in respiratory distress. He uses corticosteroid therapy starting on the sixth day of the onset of symptoms, given for 5-7 days, with the goal of preventing the inflammatory phase. Steroids are used specifically to treat those cases who on day 6 are febrile and show elevation of serologic inflammatory markers without advanced radiologic pulmonary manifestations. His initial results reportedly are excellent and admissions to the intensive care unit decreased, with shortened hospital stays and radiological and favorable clinical evolution that he has described as "spectacular" (personal communication)

In Spain and Italy this approach is gaining acceptance but at present time it is not considered standard of care. The use of steroids has been criticized because there is no evidence from randomized clinical trials to support its use for COVID-19. In addition, the anti-inflammatory medications, may delay the elimination of virus and increase the risk of secondary infection.

However, there is no evidence that, as proposed by [name], a short course of steroids given shortly before the second phase of the disease to patients at high risk of entering the inflammatory phase, has had any unfavorable impact on the disease. Thus, the concern against its use is totally based on theoretical grounds. The few data available against the use of steroids come from trials in which they have used them either too late or too early[8].

[figure not shown]
An elevated interleukin-6 (IL-6) has been strongly associated with the need for mechanical ventilation (p=.00005). In addition, the maximal IL-6 level (cutoff 80 pg./ml) for each patient during disease predicted respiratory failure with high accuracy (p=.000005, AUC=0.98). The risk of respiratory failure for patients with IL-6 levels of \geq 80 pg./ml was 22 times higher compared with patients who have lower IL-6 levels[9].

In this protocol, we propose to identify patients with Covid-19 who are at very high risk of developing cytokine storm and consequently respiratory failure. The goal is to treat them early with corticosteroids in order to determine if we can avoid the cytokine storm.

Diagnosis of Covid-19 will be established by means of either the PCR molecular test or with the rapid serologic test or both (see figure 3 below). Cases who are IgG positive but IgM negative, will not be considered eligible unless they are positive by molecular PCR test.

In addition, we propose to identify a subset of patients with low risk of complications by analyzing their markers of inflammation as well as other prognostic variables. Due to the large number of cases currently admitted to our hospital, the situation now has reached a critical point. If we could generate data that can provide guidance as to which patients can be safely managed on an outpatient basis and which ones could be discharged with little risk of complications, it could help relieve this burden.

Figure 3

Test results		lts	Clinian Cinniff
PCR	IgM	IgG	Clinical Significance
+	-	-	Patient may be in the window period of infection.
+	+	.=	Patient may be in the early stage of infection.
+	+	+	Patient is in the active phase of infection.
+	-	+	Patient may be in the late or recurrent stage of infection.
-	+	-	Patient may be in the early stage of infection. PCR result may be false-negative.
-	_	+	Patient may have had a past infection, and has recovered.
-	+	+	Patient may be in the recovery stage of an infection, or the PCR result may be false-negative.

4.0 Study Objectives and End Points

Primary Objective:

- 1- To decrease the rate of progression to hypoxemic respiratory failure in high risk patients with Covid-19, treated with prophylactic steroids during the first phase of the disease.
 - a. Hypoxemic respiratory failure is defined as:
 - 1. O_2 saturation of < 91% or pO_2 <60 on room air
- 2- To evaluate the rate of complications of patients observed without treatment.
 Complications include progression to respiratory failure or any other complication leading to hospitalization.

Secondary Objectives:

- 1. To determine % survival at 28 days from registration on this clinical trial
- 2. To determine if there is any improvement in inflammatory markers following treatment with corticosteroids.
- 3. To define the length of hospitalization
- 4. To determine the frequency of admissions to ICU.
- 5. To determine the percentage of patients who require ventilatory support.
- 6. To determine the rate of complications and progression to respiratory failure in patients with favorable features (i.e., those eligible for observation and not for therapy with methylprednisolone.)
 - a. To validate these results in an independent cohort of cases diagnosed as Covid-19 from our general hospital population.
- 7. We will evaluate the proportion of patients with clinical improvement, as defined by live discharge from the hospital, a decrease of at least 2 points from baseline on a modified ordinal scale (as recommended by the WHO R&D Blueprint Group), or both. [10]
 - 7.1 The six-point scale consists of the following categories:
 - (1) not hospitalized;

- (2) hospitalized, not requiring supplemental oxygen;
- (3) hospitalized, requiring supplemental oxygen;
- (4) hospitalized, requiring nasal high-flow oxygen therapy, noninvasive mechanical ventilation, or both;
- (5) hospitalized, requiring invasive mechanical ventilation, ECMO, or both; and
- (6) death.

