6.0 Inclusion Criteria

- 6.1 All patients diagnosed with Covid-19 will be registered on the study regardless of their severity, but only those who meet high risk criteria will be treated with steroids. Those who do not meet the criteria will only be registered with no need to collect further data except baseline labs and CT chest. They should sign the consent form and the data manager can collect the rest of the information.
- 6.2 Male or female patients of 21 years or older diagnosed with Covid-19 by PCR or by rapid serological test will be eligible. Diagnosis of Covid-19 will be established by means of either the PCR molecular test or with the rapid serologic test or both. (see figure 3)

We have learned recently that some cases produce IgG very early and presence of IgG doesn't mean that infection is late. Those who are IgM positive but PCR negative, will be considered as "suspicious for Covid-19"; however, if their clinical presentation is typical for Covid-19, (see below) they will be counted as a positive diagnosis. Those who are IgM positive but PCR negative, for purposes of analysis will be divided as "polysymptomatic" (2 or more symptoms characteristic of Covid-19) or "not polysymptomatic". The symptoms considered as characteristic are fever, cough, dyspnea, myalgia, diarrhea, anosmia/dysgeusia, malaise, headache, abdominal pain, neurological symptoms (paresthesiae, delirium etc).

- 6.2 a. Patients who have negative Covid IgG and IgM but whose PCR results are not available yet and who have typical symptoms of Covid-19 (see section 6.2 above), or who have typical CT chest findings such as ground glass opacities, will be considered eligible. If PCR later on turns to be negative, the patient will be retrospectively considered as ineligible.
- 6.3 Eligible patients will be registered on study on or before 10 days from first onset of symptoms. Patients whose symptoms started > 10 days ago; but who are not in respiratory failure are eligible if they are still symptomatic.
- 6.4 In order to be treated with methylprednisolone, they must meet at least two of the following criteria on or shortly before day 10 (but not before day 7)

 from first onset of symptoms, in order to avoid treatment during viral phase; if two criteria are met before day 7, patient is eligible but treatment should not start before day 7 of illness:
 - 6.4.1 Serum IL-6 \geq 10 pg/ml before day 10.
 - 6.4.2 Ferritin> 500 ng/ml before day 10.

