 - 6.4.3 D-dimer > 1 mg/L (1,000 ng/ml) before day 10.
 - 6.4.4 CRP > 10 mg/dL (100 mg/L) before day 10.
 - 6.4.5 LDH above normal before day 10.

- 6.4.6 Lymphopenia (absolute lymphocyte count <900) before day 10.
- 6.4.7 O₂ saturation <94% by pulse oximetry, but more than 91%, before day 10.
- 6.4.8 CT chest with evidence of infiltrate(s).
- 6.5 Interpretation of results of rapid and PCR molecular tests:
 - 6.5.1 Those with serological positive test but negative molecular PCR test will be analyzed based on the clinical context. See below.
 - 6.5.2 Those who present with at least 2 of the following typical symptoms of Covid-19 (cough, fever, dyspnea, diarrhea, anosmia) will be considered as likely cases of Covid-19 while those with one or less symptoms will be considered as unlikely cases but will still be considered evaluable. They will be analyzed separately.
 - 6.5.3 Those who are PCR positive and serology positive or negative will be considered as definitive cases.
- 6.6 The CALL score will be used in the analysis of all cases (11). This score represents a composite index based on presence of comorbidities, age >60, lymphopenia and elevated LDH. Those cases with a score >6 have greater than 50% risk for serious complications.
- 6.7 Simultaneous treatment will be allowed with the following drugs: remdesivir, hydroxychloroquine, azithromycin, vitamin C, doxycycline, colchicine, zinc and ivermectin. Patients who have received 1 single dose of dexamethasone or methylprednisolone will be eligible. **Their use is not considered as a basis for exclusion** from this trial.

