8.0 Management and Dosing Regimen

- 8.1 Patients will be admitted to a regular room in the hospital (**not** ICU)
- 8.2 They will be monitored closely with vital signs every 8 hours to ensure their respiratory and cardiovascular status do not deteriorate.
- 8.3 Methylprednisolone 80 mg IV bolus injection will be given daily x 5 days starting upon day 1-3 of registration on trial. Patients who are stable with O2 sat >94% and no other indication for hospitalization will be treated as outpatient with methylprednisolone 80 mg p.o. x 5 days.

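### The event behind the 50% success rule omits death and ventilation, has no time window and is unscheduled in treated outpatients, while patients already below the cut-off can enter; the net bias is unknown

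*Protocol*

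**What the plan says.** **Event.** In Protocol section 4.0 the first primary objective is "To decrease the rate of progression to hypoxemic respiratory failure in high risk patients with Covid-19, treated with prophylactic steroids". Failure is an oxygen "saturation of < 91% or pO_2 <60 on room air". The definition has no other component and no time window. Ventilation and death are separate secondary objectives: "To determine the percentage of patients who require ventilatory support" and "To determine % survival at 28 days from registration on this clinical trial".

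**Rule.** Section 5.4 calls the treatment successful if no more than 50% of high-risk patients develop respiratory failure. Section 5.2 expects at least 40-60 treated patients.

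**Measurement.** Section 2.1 places arterial gases and pulse oximetry at or before entry. During the study, section 2.2.1 reads "For patients admitted to hospital: Vital signs q 8 hours". The day 7-10, day 14 and day 28 assessments list blood tests, with PCR on days 14 and 28 and CT on day 28. None lists oximetry or a blood gas. Under section 8.3, stable patients with saturation above 94% and no other reason for admission "will be treated as outpatient with methylprednisolone".

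**Entry.** Section 6.4 asks for any two of eight criteria. One of them, 6.4.7, is "saturation <94% by pulse oximetry, but more than 91%, before day 10". Section 6.3 adds, only for symptoms that began more than 10 days ago, that patients "who are not in respiratory failure are eligible if they are still symptomatic". Section 7.2 excludes oxygen-dependent patients but does not define the term. No criterion sets a general lower limit on saturation or pO2.

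**Second primary measure.** Section 10.0 gives primary response criteria. Complete response requires no ventilatory support, no oxygen dependence by day 28, survival to day 28 and a near-clear CT. Partial response requires two of three items (ventilation, oxygen dependence, CT); survival is not one of them.

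**The concern.** The trial has no control arm and one stated success rule, a bare comparison of an observed proportion with 50%. Its conclusion therefore depends on who is counted as a failure, and the text leaves that open in two ways.

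First, a patient given oxygen at 92% who is later intubated or dies need never have a qualifying room-air reading, and by the definition has not failed. A treated outpatient whose saturation falls between visits may never be measured, and an unobserved failure defaults to a non-failure. Both errors lower the failure rate.

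Second, a patient at 88% on room air, within 10 days of onset and with two abnormal markers, meets the treatment criteria and already has the event. That patient counts as a failure whatever the treatment does, which raises the rate. Progression has no meaning for such a patient.

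**Working it through.** **What the document gives.** Treated n of 40-60 (5.2) and success if failures are at most 50% (5.4), that is, at most 20/40, 25/50 or 30/60. The protocol states no error rate, power or target rate, so it has no figure of its own to reproduce.

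**Weight of one patient.** 1/60 = 1.7 points; 1/40 = 2.5 points.

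**Effect of missed failures.** Assumptions, not in the documents: true failure rate p and share m of true failures that the definition or schedule does not capture. The observed rate is then p(1-m), and the chance of declared success is

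P(X ≤ n/2), with X ~ Binomial(n, p(1-m)).

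| True rate p | m | n=40 | n=50 | n=60 |
|---|---|---|---|---|
| 0.55 | 0% | 0.316 | 0.284 | 0.258 |
| 0.55 | 10% | 0.588 | 0.584 | 0.582 |
| 0.55 | 20% | 0.822 | 0.841 | 0.857 |
| 0.60 | 0% | 0.130 | 0.098 | 0.075 |
| 0.60 | 10% | 0.362 | 0.334 | 0.311 |
| 0.60 | 20% | 0.660 | 0.665 | 0.670 |
| 0.65 | 0% | 0.036 | 0.021 | 0.012 |
| 0.65 | 10% | 0.176 | 0.141 | 0.115 |
| 0.65 | 20% | 0.461 | 0.443 | 0.428 |

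At p = 0.60 the observed rate falls to 50% when m = 1 - 0.50/0.60 = 16.7%. That is 4 of 24 failures at n=40, 5 of 30 at n=50, or 6 of 36 at n=60.

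**Effect of baseline failures, opposite direction.** Assumptions: a share b of treated patients is already below the cut-off, and the others fail at rate q = 0.40. The observed rate is b + (1-b)q.

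| b | Observed rate | n=40 | n=50 | n=60 |
|---|---|---|---|---|
| 0% | 0.40 | 0.926 | 0.943 | 0.956 |
| 5% | 0.43 | 0.854 | 0.873 | 0.889 |
| 10% | 0.46 | 0.748 | 0.761 | 0.774 |
| 20% | 0.52 | 0.461 | 0.443 | 0.428 |

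**Both together.** The observed rate is b + (1-b)q(1-m). It equals q when b = qm / (1 - q(1-m)). With q = 0.60 and m = 10%, b = 0.06/0.46 = 13%; with m = 20%, b = 0.12/0.52 = 23%. A smaller b leaves a net downward error and a larger b a net upward one. The documents give neither b nor m, so the sign cannot be determined.

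**The case against.** The strongest reply is that the worst outcomes are not lost. Section 4.0 reports survival, ICU admission and ventilation as secondary outcomes, and section 10.0 builds ventilation, oxygen dependence and, for complete response, survival into criteria that it also calls primary. This is right, and a reader who inferred that the protocol ignores these outcomes would be wrong. The defect is confined to the count used in 5.4, to which nothing links section 10.0.

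A second reply is that misclassification needs a narrow path. Inpatients have vital signs every 8 hours, and many patients who reach ventilation or death would first have a reading below 91%. Outpatients start above 94% and, once admitted, come under the inpatient schedule. This stands as a limit on size: the share missed may be small. It would also be too strong to say that outpatients are unmonitored. The day 7-10, 14 and 28 assessments cover every treated patient, and section 10.0 needs each patient's oxygen status by day 28. What is missing is scheduled oximetry or a blood gas.

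The room-air condition may attach only to pO2. Even so, a patient kept at 91% or above on oxygen or a ventilator is not counted.

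On entry, section 7.2 may remove patients already on oxygen, and the word progression implies freedom from the event at baseline. The gap is therefore mainly patients below the cut-off on room air within 10 days of onset, but no criterion closes it.

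**Conclusion.** The point holds as a statement of what the text permits. The 5.4 event omits death and ventilatory support, has no window, and has no scheduled post-entry measurement in treated outpatients; these gaps favour declaring success. Admission of patients already below the cut-off works against it. A reader might infer that the failure rate is biased downward overall. The documents do not support that, because the two errors oppose each other and neither share is known.

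The size is unknown too. Only the 1.7 to 2.5 points per patient follows from the document. The probabilities of declared success rest on assumed true rates and assumed shares missed or failing at entry, and they show sensitivity rather than an expected error. They do show that, with a bare 50% cut-off and 40-60 patients, four to six misclassified patients can decide the result. Because this is the event on which success is declared, it should be settled before analysis.

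**What to change.** - Define failure by day 28 from registration as the first of: room-air saturation <91% or pO2 <60; high-flow oxygen; non-invasive or invasive ventilation; death.
- Add a sensitivity analysis that also counts new supplemental oxygen (category 3 on the protocol's six-point scale), since ordinary oxygen can mask a room-air fall.
- For all treated patients, record oximetry, and any oxygen use or admission since the last contact, at the existing day 14 and day 28 visits. A brief fall between visits in an outpatient who is neither admitted nor given oxygen will still be missed.
- Keep the evaluable set of section 12.0 (at least one dose). List patients who meet the definition before first dose and show the rate with and without them.
- State that the 50% benchmark in 5.3 and 5.4 refers to this same event. Section 5.3 speaks of respiratory insufficiency and 5.4 of respiratory failure; widening the event without checking the benchmark would break the comparison.
- Say how section 10.0 relates to 4.0 and 5.4, and reconcile the entry wording in 6.3, 6.4.7 and 7.2.

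The cost is revised wording, one oximetry reading and a short question at visits that already take place, and a somewhat higher reported failure rate.

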7.0 Exclusion Criteria

- 7.1 Any patient with life expectancy <1 month
- 7.2 Any patient who is oxygen dependent
- 7.3 Any patient with long standing history of severe COPD

- 7.4 Any patient who is chronically oxygen dependent because of previously existing lung disease
- 7.5 Anyone with severely uncontrolled diabetes despite adequate management.
- 7.6 Anyone with active serious bacterial infection such as septicemia or pneumonia.
- 7.7 Anyone receiving Tocilizumab (anti-IL-6 therapy) or plasma therapy
- 7.8 Any patient already receiving steroids for another pre-existing illness
- 7.9 Cases who are IgG positive but IgM negative, will not be considered eligible unless they are positive by molecular PCR test or symptoms are highly suggestive of Covid-19 (> 3 of the following: cough, dyspnea, anosmia, diarrhea, myalgia, ground glass infiltrate(s) in CT chest) within first 10 days of illness.

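### Secondary Objective 7 (clinical improvement) does not fit the treated population: its 2-point fall is unreachable or redundant, and it misclassifies treated outpatients

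*Protocol*

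**What the plan says.** Secondary Objective 7 (Protocol, section 4.0) evaluates "the proportion of patients with clinical improvement, as defined by live discharge from the hospital", or "a decrease of at least 2 points from baseline on a modified ordinal scale", or both. The scale has six categories. The three best are "1) not hospitalized", "2) hospitalized, not requiring supplemental oxygen" and "3) hospitalized, requiring supplemental oxygen"; categories 4 and 5 are higher levels of respiratory support, and 6 is death.

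Who can enter, and where they start, is set elsewhere:

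- Section 7.2 excludes "Any patient who is oxygen dependent". Section 7.4 separately excludes chronic oxygen dependence from earlier lung disease.
- Section 8.1 places patients in a regular ward room, not the ICU.
- Section 8.3 provides that stable patients with saturation above 94% "and no other indication for hospitalization will be treated as outpatient".
- Section 6.1 registers all diagnosed patients whatever their severity, but limits steroids to those who meet the high-risk criteria.
- Section 6.4.7 accepts, as one of those criteria, a saturation below 94% but above 91%.

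The protocol does not define oxygen dependence, and does not say whether baseline means registration or first dose.

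**The concern.** The trial asks whether early treatment keeps patients from getting worse. Objective 7 asks whether they get better by two steps on a scale whose best value most of them already hold or nearly hold. A patient can fall two points only from category 3 or worse, and 7.2 appears to remove those patients at entry.

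At stake is what the reported proportion would mean. If one half of the definition cannot contribute, the result is a discharge rate under another name. If treated outpatients are counted, a course with no deterioration is scored as a failure. The rate would then shift with the share treated at home, which may differ between hospitals if other institutions join, as section 5.1 allows.

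**Working it through.** The protocol gives no expected rate, sample size or test for this endpoint, so there is no figure to reproduce. The check is an enumeration of the scale, then a ceiling on the rate.

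**Step 1: what 7.2 means.** Two features suggest that it covers current oxygen need. Section 7.4 already deals with chronic dependence, so a chronic-only reading would leave 7.2 with little to do. Section 10.0.1.2 uses the same term for a patient's status by day 28. On this reading inpatients start at category 2, "hospitalized, not requiring supplemental oxygen", and outpatients at category 1.

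**Step 2: largest possible fall.** For baseline category b and best category 1, the largest fall is b - 1.

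| Baseline b | Largest fall | End states with a fall of 2 or more | Of these, not already live discharge |
|---|---|---|---|
| 1 | 0 | none | none |
| 2 | 1 | none | none |
| 3 | 2 | 1 | none |
| 4 | 3 | 1, 2 | 2 |
| 5 | 4 | 1, 2, 3 | 2, 3 |

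- 7.2 as current oxygen need (b = 1 or 2): no patient can meet the 2-point criterion.
- 7.2 tolerating low-flow oxygen (b up to 3): only 3 to 1 qualifies. A living patient who moves from hospital to category 1 has been discharged alive, so the criterion adds nobody.
- 6.1 taken alone, against 7.2 (b up to 5): only here does the criterion add patients, through 4 to 2, 5 to 3 or 5 to 2.

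**Step 3: treated outpatients.** At b = 1 the largest fall is 0, and a patient never admitted has no hospital discharge. One who stays well is therefore not improved. One who worsens, is admitted and leaves alive meets the discharge criterion.

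**Step 4: size of the effect on the rate.** Let q be the outpatient share of treated patients and r the fraction of outpatients who are admitted and later discharged alive. Take all treated patients as denominator and suppose every inpatient is discharged alive. Then

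rate = (1 - q) + q × r.

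With r = 0 this is 1 - q. The protocol does not give q, so the values below are assumptions, applied to the 40 to 60 treated patients expected in section 5.2.

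| Assumed q | Ceiling 1 - q | Of 40 | Of 60 |
|---|---|---|---|
| 10% | 90% | 36 | 54 |
| 25% | 75% | 30 | 45 |
| 50% | 50% | 20 | 30 |

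The term q × r has the wrong sign for a prevention trial. At q = 25% the rate is 0.75 + 0.25 × 0 = 75% if every outpatient stays well, and 0.75 + 0.25 × 1 = 100% if every outpatient deteriorates, is admitted and leaves alive.

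**The case against.** The strongest reply is that the defect depends on choices the protocol leaves open. Oxygen dependence is undefined, 6.1 speaks of any severity, and 6.4.7 admits saturations just below 94%. Treatment begins on day 1 to 3 of registration and not before illness day 7, so a patient might need low-flow oxygen by first dose. This stands: it cannot be said that the 2-point fall is out of reach from every conceivable baseline. But the gain is small. From category 3 the criterion only duplicates discharge, and it needs category 4 or 5 at baseline to matter.

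A second reply is that Objective 7 does not name its denominator, that a discharge endpoint naturally suggests inpatients, and that denominator and time window may be settled in an analysis plan not shown here. This also stands in part. Section 12.0 points the other way, since anyone with at least one dose is evaluable, but the ceiling of 1 - q remains conditional on that denominator.

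Third, worsening is already covered by the primary objective and by the secondary objectives on ICU admission, ventilatory support and 28-day survival. That limits the harm but does not make Objective 7 interpretable.

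A reader might infer more than the text supports:

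- *Treated outpatients can never improve.* Not so: one who is admitted and discharged alive counts.
- *The rate says nothing about the drug.* Discharge of inpatients may respond to treatment.
- *The scale was meant only for patients already on oxygen.* The protocol says only that it is a modified version of a WHO-recommended scale, and two of its categories involve no oxygen.

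**Conclusion.** The point holds in a limited form. On the better reading of 7.2 no treated patient can meet the 2-point criterion; on the looser reading that tolerates category 3 it is redundant with live discharge. For inpatients Objective 7 is therefore live discharge, with no time point stated in the protocol.

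For outpatients the classification runs backwards if all treated patients are counted. The 90% to 50% ceiling rests on three assumptions: that denominator, an outpatient share of 10% to 50%, and no outpatient admitted. It is not a figure of the protocol.

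The consequence is confined to one secondary endpoint of an exploratory pilot. The success rule in section 5.4 uses respiratory failure alone and is untouched. The objective should still be changed, because a proportion reported under the present definition could mislead and the correction is inexpensive.

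**What to change.** 1. State whether baseline is registration or first dose. Define oxygen dependence in 7.2 and reconcile it with 6.1, so that the possible starting categories are explicit. Which patients should be eligible is for the investigators to decide.
2. Drop the 2-point criterion from Objective 7.
3. Report live discharge by day 28 only among patients hospitalized at baseline.
4. For all treated patients, report worsening on the same six categories by day 28, with the day-14 and day-28 distributions. Give these separately for patients starting as inpatients and as outpatients: a rise of one category is an admission for an outpatient (1 to 2) but a new oxygen need for an inpatient (2 to 3), so a pooled figure would again depend on the mix.

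The cost is small but more than wording. Hospital and oxygen status must be recorded at days 14 and 28, which the schedule in section 2 does not list. Much of this is needed already: Secondary Objective 3 requires length of stay, and section 10.0.1.2 requires oxygen status by day 28.
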